23.2.14 Withdrawal from Treatment

When a participant withdraws from study it is not necessary to also fill out a “withdrawal from treatment” form. Thus, some participants will only have entered information about withdrawal from study. However, when a participant withdraws from study prior to receiving the fourth infusion with eptinezumab, a withdrawal from study is also relevant to be regarded as a withdrawal from treatment. Therefore, when a participant withdraws from study prior to receiving the fourth infusion and if there is no withdrawal from treatment for that participant the withdrawal from study will be used to define withdrawal from treatment. The time of withdrawal from treatment will be the same as the time of withdrawal from study. If the primary reason for withdrawal from study is either “lack of efficacy” or “adverse events” then the primary reason for withdrawal from treatment will be the same as the primary reason for withdrawal from study. All other primary reasons for withdrawal from study will be defined as “other” for the primary reason for withdrawal from treatment. All other reasons for withdrawal will not be inherited from withdrawal from study to withdrawal from treatment. When the “Withdrawal from treatment” form was filled out all reasons for withdrawal from treatment will be used.

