8.7 Withdrawal Visit

Three different scenarios can occur, depending on whether the patients withdraw from the study, from treatment or withdraw their consent.

Patients who withdraw from the study prior to the Completion Visit (Week 48/Visit 14), except for those who withdraw their consent, will be asked to attend a Withdrawal Visit as soon as possible and a further SFU Visit, scheduled 20 weeks (5 half-lives) after the last eptinezumab administration.

Patients who are withdrawn from the treatment prior to the Completion Visit (Week 48/Visit 14) will be given the opportunity to remain in the study at the discretion of the investigator. Patients will be expected to attend all scheduled study visits and procedures except eptinezumab administration. If patients refuse, they will be asked to attend a Withdrawal Visit as soon as possible and a further SFU Visit, scheduled 20 weeks (5 half-lives) after the last eptinezumab administration.

No new information will be collected from patients who withdraw from the study or decide to withdraw, except information collected in relation to the scheduled Withdrawal Visit and SFU Visit or needed for the follow-up of adverse events (section 10.5).

The reason for withdrawal must be recorded in the eCRF, and the investigator must ask specifically whether withdrawal was due to an adverse event.

For a patient who withdraws consent:

- if the patient withdraws consent during a site visit and then agrees to it being the final visit, the investigator will complete the visit as a Withdrawal Visit and all the data collected up to and including that visit will be used;
- if the patient withdraws consent during a telephone conversation, the investigator will ask the patient if he or she will attend a Withdrawal Visit. If the patient:
 - agrees to attend a Withdrawal Visit, all the data collected up to and including that visit will be used;
 - refuses to attend a Withdrawal Visit, the investigator should attempt to follow the patient's safety and future treatment; any information collected will only be recorded in the patient's medical records;
- if the patient explicitly requests that the patient's data collected from the time of withdrawal of consent onwards not be used, this will be respected.

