13.5.5 Intercurrent Events and Withdrawal from Treatment

The number of participants who experienced the intercurrent event “use of transitional treatment” and “interruption or termination of IMP such that full dose is not received” during Weeks 1-4 will be summarized for the short-term efficacy estimand defined in sections [13.5.1](#) and [13.5.2](#).

The number of participants who experienced the intercurrent events “use of transitional treatment”, “interruption or termination of IMP such that full dose is not received” and “withdrawal from treatment” during Months 1-12 will be summarized for the long-term efficacy estimand following the definition in section [13.5.3](#).

The number of participants who withdrew from treatment will be summarized by primary reason for withdrawal and all reasons for withdrawal.

Participants who withdrew from treatment will be listed and the listing will include the number of days in the trial until withdrawal from treatment, the number of days since the last IMP, and the primary reason for withdrawal, and all reasons for withdrawal.

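### Treatment withdrawals derived from the study-withdrawal record keep a single reason, so the all-reasons table in SAP 13.5.5 can understate adverse events and lack of efficacy as contributing reasons

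*SAP*

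**What the plan says.** SAP 23.2.14 (Withdrawal from Treatment) starts from how the forms are used: "When a participant withdraws from study it is not necessary to also fill out a" treatment-withdrawal form, and so "Thus, some participants will only have entered information about withdrawal from study". The derivation applies "when a participant withdraws from study prior to receiving the fourth infusion and if there is no withdrawal from treatment for that participant". It treats the recorded reasons in three ways:

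- A primary reason of adverse events or lack of efficacy is copied across unchanged: "then the primary reason for withdrawal from treatment will be the same as the primary reason for withdrawal from study".
- For the remainder, "All other primary reasons for withdrawal from study will be defined as" 'other'.
- On non-primary reasons: "All other reasons for withdrawal will not be inherited from withdrawal from study to withdrawal from treatment".

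Where the treatment-withdrawal form was completed, the same section uses every reason on it.

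SAP 13.5.5 then plans this output: "The number of participants who withdrew from treatment will be summarized by primary reason for withdrawal and all reasons for withdrawal". A participant listing with the same two columns follows. SAP 8.2 plans a table and listing of study withdrawals, also by primary and by all reasons, with no recoding. Protocol 8.7 requires the reason for withdrawal to be recorded and says that "the investigator must ask specifically whether withdrawal was due to an adverse event".

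**The concern.** The 13.5.5 output promises all reasons, but a derived record can hold only one. Take a participant whose primary reason is withdrawal of consent and who also gave an adverse event. With a treatment-withdrawal form, the adverse event appears in the all-reasons column. Without one, the participant appears only under 'other'. How complete a row is depends on which form the site filled in, not on what happened to the participant, and the plan has no footnote or count to show which rows are truncated.

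The loss runs one way: a contributing adverse event or lack of efficacy can disappear but cannot be added. SAP 8.2 reports the same participant with all reasons, so the report can hold two tables that disagree about one person. What is at stake is an accurate count of why participants stopped eptinezumab, in a trial whose primary objective is long-term safety and tolerability.

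**Working it through.** **The plan's own figure.** Protocol 16.11 and SAP 20 plan for 100 completers at 20% withdrawal: 100 / (1 − 0.20) = 125. This reproduces the planned number exactly and implies 125 − 100 = 25 withdrawals. The point here does not dispute that figure.

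**What the rule does.** The 23.2.14 rule was applied to eight constructed participants, all with a study-withdrawal record only. AE is adverse events and LoE is lack of efficacy.

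| Primary reason | Other recorded reasons | All-reasons entry under 23.2.14 | Entry if non-primary reasons are carried over |
|---|---|---|---|
| AE | none | AE | AE |
| LoE | none | LoE | LoE |
| AE | LoE | AE | AE, LoE |
| LoE | AE | LoE | LoE, AE |
| Consent | none | other | other |
| Consent | AE | other | other, AE |
| Consent | LoE | other | other, LoE |
| Lost to follow-up | AE, LoE | other | other, AE, LoE |

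All-reasons counts are AE 2 and LoE 2 under the rule, against AE 5 and LoE 5 with carry-over. Every missed count is a non-primary reason. The primary-reason counts of AE and LoE are 2 and 2 either way. The cases were chosen to show the mechanism and say nothing about frequency.

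**Possible size in this trial.** The documents do not say how many withdrawals will have a derived record, or how often AE or LoE is recorded as non-primary. Let f be the assumed share of the 25 withdrawals with a derived record, and g the assumed share of those with a given reason (AE or LoE) recorded as non-primary. The undercount for that reason is 25 × f × g.

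| | g = 0 | g = 0.1 | g = 0.2 | g = 0.5 |
|---|---|---|---|---|
| f = 0.25 | 0 | 0.625 | 1.25 | 3.125 |
| f = 0.5 | 0 | 1.25 | 2.5 | 6.25 |
| f = 1 | 0 | 2.5 | 5.0 | 12.5 |

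As a share of 125 treated, 1.25 is 1.0%, 5.0 is 4.0% and 12.5 is 10.0%. The row f = 1 is a ceiling at the planned rate. It needs every withdrawal to come before the fourth infusion and none to have a treatment-withdrawal record.

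**Which outputs use the dropped reasons.**

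- The 13.5.5 all-reasons table and the matching listing column use them.
- The 13.5.5 primary-reason counts of AE and LoE do not, because those reasons are copied.
- The long-term estimand (13.5.3) does not, because its intercurrent event is defined on the primary reason only.
- The 8.2 table and listing do not, because they take study-withdrawal reasons directly.
- The summaries and listing of adverse events leading to withdrawal (14.1.4, 14.1.8) do not; nothing in those sections refers to the 23.2.14 derivation.

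**The case against.** The strongest reply is that no recorded reason is lost from the report. Every derived record belongs to someone who withdrew from the study, so each treated participant affected is in the 8.2 table and listing with all reasons intact. Participants who stop treatment but stay in the study are not in 8.2, but they are not derived cases, and where their form is completed all its reasons are used. Tolerability is also assessed mainly through chapter 14, which reports adverse events leading to withdrawal separately. The affected table sits in the efficacy chapter beside the intercurrent-event counts, and the estimand needs only the primary reason, which the rule preserves.

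Most of this stands. A reader might infer that adverse events as reasons for stopping eptinezumab vanish from the results, or that the primary safety analysis is biased. The documents do not support either inference. What remains is that 13.5.5 is the planned tabulation of reasons for stopping treatment, it is labelled as covering all reasons, and for derived records it does not. The 8.2 table is not a like-for-like replacement, because it also includes people who leave after the fourth infusion and leaves out those who stop treatment but remain in the study. Section 14.1.8 has no counterpart for lack of efficacy.

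Two further replies are fair. Protocol 8.7 requires a specific question about adverse events but none about lack of efficacy, so how fully the latter is recorded as a secondary reason is uncertain. Recoding other primary reasons to 'other' is also defensible: Protocol 6.2 sets different criteria for study and treatment withdrawal, so changing that part would be a matter of preference.

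**Conclusion.** The point holds in a limited form. For derived treatment withdrawals, 23.2.14 drops non-primary reasons, so the all-reasons table and listing column in 13.5.5 combine complete and single-reason records. They can understate adverse events and lack of efficacy as contributing reasons, and they can conflict with 8.2 for the same participants.

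It would be too strong to say that reasons in general are not carried over, since a primary reason of adverse events or lack of efficacy is. It would also be too strong to say that the table will undercount. That needs at least one derived record with one of these as a non-primary reason, and the documents give no frequency. The range of 0 to 12.5 participants per reason rests on the planned 25 withdrawals and on assumed shares; zero is possible. No estimand, primary endpoint or output on adverse events leading to withdrawal changes. This is a correction to one reporting rule, worth making because it costs little.

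**What to change.** In SAP 23.2.14, replace the sentence on non-inherited reasons with a rule that the non-primary reasons on the study-withdrawal form, at least adverse events and lack of efficacy, are carried over to the derived treatment-withdrawal record. Leave the primary-reason rule as it is, so the intercurrent event in 13.5.3 is defined exactly as now. Add a footnote to the 13.5.5 table giving the number of derived records.

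No new data are needed. The cost is one changed sentence, one footnote and minor reprogramming. The reason categories on the two forms may differ, and the documents do not show the code lists, so some mapping may be required.

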23.3 Assigning Data to Visits

See section [3.1](#) for definition of baseline values.

23.3.1 Clinical Outcome Assessments (COAs) - Scales

For a participant withdrawing prior to the Completion Visit, the Withdrawal Visit will also include efficacy evaluations (PGIC, SIS, EQ-5D-5L, HCRU, and WPAI:GH2.0).

Assessments from PGIC will be assigned to a Visit based on the windowing in [Panel 8](#).

Assessments from SIS will be assigned to a Visit based on the windowing in [Panel 9](#).

Assessments from EQ-5D-5L, HCRU, and WPAI:GH2.0 will be assigned to a Visit based on the windowing in [Panel 10](#). In case of duplicate scale assessments in relation to a nominal visit the assessments from the Withdrawal Visit will be used.

Panel 8 Visit Windows – PGIC

Nominal Visit Number	Nominal Visit Week	Nominal Visit Day	Time Window
Visit 3	4	28	1-42
Visit 4	8	56	43-70
Visit 5	12	84	71-98
Visit 6	16	112	99-126
Visit 7	20	140	127-154
Visit 8	24	168	155-182
Visit 9	28	196	183-210
Visit 10	32	224	211-238
Visit 11	36	252	239-266
Visit 12	40	280	267-294
Visit 13	44	308	295-322
Visit 14	48	336	> 322

Panel 9 Visit Windows – SIS

Nominal Visit Number	Nominal Visit Week	Nominal Visit Day	Time Window
Visit 3	4	28	1-56
Visit 5	12	84	57-98
Visit 6	16	112	99-140
Visit 8	24	168	141-182
Visit 9	28	196	183-224
Visit 11	36	252	225-266
Visit 12	40	280	267-308
Visit 14	48	336	>308

Panel 10 Visit Windows – EQ-5D-5L, HCRU, and WPAI:GH2.0

Nominal Visit Number	Nominal Visit Week	Nominal Visit Day	Time Window
Visit 3	4	28	<84
Visit 6	16	112	84 <= and <168
Visit 9	28	196	168 <= and < 252

Nominal Visit Number	Nominal Visit Week	Nominal Visit Day	Time Window
Visit 12	40	280	252 <= and < 308
Visit 14	48	336	308 <=

Unscheduled visits will not contain assessments of the COAs mentioned above. In relation to the nominal visits post-baseline, a participant can complete their COAs 3 days before the visit. In case of duplicate scale assessments in relation to a nominal visit, i.e. if a participant fills out the scales 3 days before the visit and the visit is postponed afterwards implying that the participant has to complete the COA again, the latest assessment will be used.

Assessments done at Visit 2 for EQ-5D-5L, SIS, HCRU, and WPAI:GH2.0 will be assigned as the baseline value regardless of timing in relation to the IMP infusion.

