
• To evaluate the efficacy of eptinezumab on health-related quality of life, health care resource utilization, and work productivity	
• Endpoints for the secondary objective:
– Change from baseline in EuroQol 5-Dimension 5-Level (EQ-5D-5L) at Weeks 4, 16, 28, 40 and 48– Health Care Resources Utilization (HCRU) at baseline, Weeks 4, 16, 28, 40 and 48– Change from baseline in the Work Productivity Activity Impairment: General Health second version (WPAI:GH2.0) sub-scores (Absenteeism, Presenteeism, Work productivity loss, Activity impairment) at Weeks 4, 16, 28, 40 and 48
Exploratory Objective 
• To explore the target engagement of eptinezumab to CGRP	
• Endpoint for the exploratory objective:
– Change from baseline to each study time point in CGRP: CGRP-eptinezumab complex, free CGRP

3 Study Design

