23.2.12 Health Care Resource Utilization (HCRU)

Cluster headache-specific healthcare resource utilization information will be collected in terms of outparticipant health care professional visits, emergency room visits, hospital admissions as well as number of overnight hospital stays during the past 4 weeks. Clinical site personnel and participants will be instructed to capture utilization that takes place outside of visits associated with their participation in the clinical trial.

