23.3.2 Safety Variables

If there is more than one assessment at a visit (either due to multiple assessments or because an unscheduled or withdrawal visit assessment is mapped to a nominal visit with an already existing value) the value that will be used in summary tables by visit will be the one closest to the nominal day for the visit but prioritizing values from scheduled visits above values from withdrawal or unscheduled visits. In the ordering of multiple values, assessments without recorded time will come after assessments with recorded time and the first in the ordering will be picked.

Laboratory Tests and ECG

Assessments of laboratory tests and ECGs at unscheduled visits and withdrawal visits will be assigned to a nominal visit according to the visit windowing specified in [Panel 11](#) for participants in the APTS. Assessments for participants not receiving any infusions of IMP will be assigned to the Baseline Visit.

Panel 11 Visit Windows – Laboratory tests, ECG

Nominal Visit Number	Nominal Visit Week	Nominal Visit Day	Time Window
Visit 1 (Screening Visit)	-4	-28	Before day 0 and before first IMP infusion
Visit 2 (Baseline Visit)	0	0	Same day as first IMP infusion (Day 0) and prior to IMP infusion on that date
Visit 5	12	84	After start of first IMP infusion to start of Visit 5 IMP infusion
Visit 8	24	168	After start of Visit 5 IMP infusion to start of Visit 8 IMP infusion

Nominal Visit Number	Nominal Visit Week	Nominal Visit Day	Time Window
Visit 11	36	252	After start of Visit 8 IMP infusion to start of Visit 11 IMP infusion
Visit 14	48	336	After start of Visit 11 IMP infusion

Vital Signs

Vital signs will be assessed before and after infusion at nominal visits. For unscheduled or withdrawal visit assessments of vital signs, the values will be assigned a nominal visit according to [Panel 12](#), and for scheduled visits where no IMP was given the assessment will be windowed to the pre-dose assessment at the nominal visit.

Panel 12 Visit Windows – Vital Signs (Pulse rate, Blood Pressure, Temperature)

Nominal Visit Number	Nominal Visit Week	Nominal Visit Day	Time Window
Visit 1 (Screening Visit)	-4	-28	Before day 0 and before first IMP infusion
Visit 2 (Baseline Visit) pre-dose	0	0	Same day as first IMP infusion (Day 0) and prior to IMP infusion on that date
Visit 2 (Baseline Visit) post-dose	0	0	After start of first IMP infusion to day 42
Visit 5 pre-dose	12	84	Day 43 to start of Visit 5 IMP infusion

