- f At the Screening Visit, the participant will be asked to sign the main Informed Consent Form (ICF), and the ICF for blood sampling for pharmacogenetics (optional). Depending of the country requirements, the number of ICFs may be different. Under exceptional circumstances, the discussion with the participants about the Informed Consent Form(s) can be done as a virtual clinic visit and the Informed Consent Form(s) can be provided remotely in line with the US FDA and EMA guidances. According to the EMA guidance, this could comprise contacting the participants via phone or video-calls and obtaining oral consents, to be documented in the participants' medical records, supplemented with email confirmation. Any consent obtained this way should be documented and confirmed by way of normal consent procedures at the earliest opportunity when the participants are back at the clinical sites.
- g Participants must have adequately documented records or reliable history of cCH and previous treatment for cCH within the 12 months prior to the Screening Visit. See protocol (section 12) for definition of adequately documented records.
- h During the Treatment Period, ePROs which are scheduled in alignment with a clinic visit can be completed in the clinic or in the remote setting within 3 days prior to the scheduled clinic visit date. ePROs which are scheduled in alignment with a phone contact must be completed in the remote setting and can be completed on the day or within 3 days prior to the scheduled phone contact date.
- i At the Screening Visit, the participant must be assisted with the provisioning and training of the eDiary and ePROs. Details will be provided in a separate training module.
- j Participants must complete the eDiary daily during the Screening Period (from Week -4 to Day 0) and during the first 4 weeks that follow each eptinezumab infusion (Weeks 1 to 4, 13 to 16, 25 to 28, and 37 to 40) and weekly for Weeks 5 to 12, 17 to 24, 29 to 36, and 41 to 48.
- k Participants must complete the daily eDiary and ePRO entries prior to infusion and prior to any interaction with the clinical site staff.
- l In addition to the eDiary compliance checks performed at the defined trial visits, ongoing evaluation of eDiary compliance will be performed by the clinical site (based on eDiary reporting) and more frequent contact with participants may be performed in case of non-compliance.

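### SAP 23.3.1 lets a Withdrawal Visit questionnaire replace one completed on schedule, so EQ-5D-5L, HCRU and WPAI values analysed as Week 4, 16 or 28 can be up to 55 days late (27 days at Week 40)

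*SAP*

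**What the plan says.** The Protocol (Section 2, Panel 3) ties the health-economic endpoints to fixed times, for example "Change from baseline in EuroQol 5-Dimension 5-Level (EQ-5D-5L) at Weeks 4, 16, 28, 40 and 48". HCRU and the WPAI:GH2.0 sub-scores use the same weeks. Weeks 4, 16, 28 and 40 are phone contacts four weeks after each infusion, with a visit window of ±3 days. Their questionnaires "can be completed on the day or within 3 days prior to the scheduled phone contact date" (SAP Appendix IV, note h), so the intended timing is tight.

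SAP 23.3.1 adds that a participant who withdraws before the Completion Visit also completes PGIC, SIS, EQ-5D-5L, HCRU and WPAI:GH2.0 at the Withdrawal Visit. Assessments are placed by Panel 8 (PGIC), Panel 9 (SIS) or Panel 10 (the other three). Directly after the reference to Panel 10 comes the clash rule: "In case of duplicate scale assessments in relation to a nominal visit the assessments from the Withdrawal Visit will be used".

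A second rule, below Panel 10, deals with a questionnaire filled in ahead of a visit that is then postponed, "implying that the participant has to complete the COA again, the latest assessment will be used".

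For safety variables, SAP 23.3.2 faces the same situation, a withdrawal assessment mapped to a visit that already has a value. There it takes the value closest to the nominal day while "prioritizing values from scheduled visits above values from withdrawal or unscheduled visits".

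**The concern.** Take a participant who completes the questionnaires on Day 28 and attends a Withdrawal Visit on Day 80. Panel 10 keeps the Week 4 window open until Day 83, so both sets fall in Week 4. The clash rule then drops the Day 28 set and analyses the Day 80 set as Week 4.

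The recall periods make this more than a labelling detail. HCRU asks about "hospital admissions as well as number of overnight hospital stays during the past 4 weeks", so this Week 4 entry would describe about Days 52 to 80 instead of Days 0 to 28, with no overlap. WPAI:GH2.0 recalls seven days, so its two periods do not overlap either.

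The rule discards a valid observation at the stated time point and replaces it with one made near the end of a dosing cycle, as the participant leaves the study. This happens only in participants who withdraw. SAP 13.5.7 prefers the MMRM partly because it can use the data of those who withdraw, and deleting their on-time values works against that.

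**Working it through.** **Planned withdrawals.** SAP chapter 20 wants 100 completers with 20% withdrawal: 100 / (1 − 0.20) = 125, which reproduces the planned number. Planned withdrawals are 125 − 100 = 25.

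**Maximum lag, Panel 10** (last day of window minus nominal day):

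| Visit | Nominal day | Last day of window | Maximum lag |
|---|---|---|---|
| Week 4 | 28 | 83 | 55 days |
| Week 16 | 112 | 167 | 55 days |
| Week 28 | 196 | 251 | 55 days |
| Week 40 | 280 | 307 | 27 days |

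For comparison, an on-time phone-visit questionnaire lies between about 6 days before the nominal day (3 for the visit window plus 3 for early completion) and 3 days after it.

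**Maximum lag, Panels 8 and 9, if the sentence covers them.** SIS: 28 days at Weeks 4, 16, 28 and 40 (for example 56 − 28) and 14 days at Weeks 12, 24 and 36 (for example 98 − 84). PGIC: 14 days at each of Weeks 4 to 44. Weeks 12, 24 and 36 are infusion visits, with the scheduled questionnaire completed before dosing. A Withdrawal Visit on Days 85–98, 169–182 or 253–266 would replace that pre-infusion value with a post-infusion one.

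**How many values.** The documents do not give the number of clashes. Assume 25 withdrawals, Withdrawal Visits spread evenly over Days 1 to 335 (the Completion Visit is Day 336), every withdrawer attending, and every scheduled questionnaire completed on its nominal day. A clash then occurs on any day after the nominal day but still inside its window.

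- Panel 10: 55 + 55 + 55 + 27 = 192 days; 192/335 = 57%; × 25 = 14.3 participants.
- By visit: 55/335 × 25 = 4.1 at each of Weeks 4, 16 and 28; 27/335 × 25 = 2.0 at Week 40.
- Average lag among these: (3 × 1,540 + 378)/192 = 4,998/192 = 26 days, where 1,540 is the sum of 1 to 55 and 378 the sum of 1 to 27.
- Panel 9, if covered: 28 + 14 + 28 + 14 + 28 + 14 + 28 = 154 days; 154/335 = 46%; × 25 = 11.5.
- Panel 8, if covered: 11 × 14 = 154 days; again 11.5.
- With half of withdrawers attending, the Panel 10 total falls to 14.3 × 0.5, about 7.

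**Effect on a mean.** If k of n values at a visit are replaced and the replacements differ from the dropped values by d on average, the raw mean shifts by (k/n) × d. With n between 100 and 125, k/n is 4.1/125 = 3.3% to 4.1/100 = 4.1% at Weeks 4, 16 and 28, and 2.0/125 = 1.6% to 2.0/100 = 2.0% at Week 40. The shift is thus about 2% to 4% of d. The documents do not give d or its sign.

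**Which analyses.** SAP 13.5.6.1 fits the MMRM to the EQ-5D-5L VAS, WPAI:GH2.0 sub-scores, SIS domains and PGIC. HCRU is not listed there, so under 13.5.6.3 it is only summarised descriptively.

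**The case against.** The best defence is that keeping the last report a participant gives on study is a legitimate pre-specified choice, and that efficacy and safety data may follow different precedence rules. The second part stands: 23.3.1 and 23.3.2 differ but do not contradict each other. The first part does not meet the point. The last report is not analysed as a last report; it is moved back to an earlier time point, and what was observed there is removed. The SAP gives no reason for this.

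The defence is right about size. The count is a ceiling: participants lost to follow-up may never attend, those who withdraw consent are outside the standard request, and those withdrawn from treatment may stay on scheduled visits (Protocol 6.2 and 8.7). Many replacements would be only days late.

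Several stronger readings are tempting but unsupported:

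- That Week 40 values can also be 55 days late. The window closes at Day 307, so 27 is the limit.
- That about 14 values are replaced at a visit. That is the total over four visits.
- That the visit means cease to measure their time point. A replacement share of 2% to 4% does not show this.
- That the HCRU recall problem biases a modelled estimate. HCRU is not modelled.
- That SIS and PGIC are certainly affected. The sentence follows the Panel 10 reference and can be read as limited to those scales, although its wording is general.

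The postponed-visit rule does not rescue the scheduled value. It concerns repeats for a postponed visit and, if applied more widely, would also select the later Withdrawal Visit value.

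**Conclusion.** The rule as written replaces on-time EQ-5D-5L, HCRU and WPAI:GH2.0 values with Withdrawal Visit values taken up to 55 days late at Weeks 4, 16 and 28, and up to 27 days late at Week 40. This follows from the text and Panel 10 alone. Whether SIS (up to 28 days) and PGIC (up to 14 days) are included depends on how the sentence is read.

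The likely numerical effect is small: at most about 4, 4, 4 and 2 replaced values at the four visits, given 25 withdrawals, even timing, full Withdrawal Visit attendance and complete scheduled data. These are secondary endpoints in a single-arm study with no formal testing and a primary objective of safety. The change is still worth making, because the error falls only on participants who withdraw and the SAP already contains a better rule.

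**What to change.** In SAP 23.3.1, replace the Withdrawal Visit sentence with the priority used in 23.3.2: the scheduled assessment is used for its nominal visit; a Withdrawal Visit assessment is used only when the window holds no scheduled value, and is otherwise listed only. State which scales the rule covers. Limit the latest-assessment sentence to repeat completions for the same scheduled visit.

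The displaced value should not be carried to the next visit. A Day 29 value would then stand for Week 16 (Day 112), which is 112 − 29 = 83 days early and worse than the present lag. It would also represent four weeks after a second infusion that the participant never received.

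The cost is two sentence edits and no new data. Some Withdrawal Visit values will be listed but not analysed. Where no scheduled value exists, a late value can still enter the window, because the Panel 10 windows stay as wide as they are.
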